11.1. Recruitment and informed consent procedures

Eligible patients will be recruited from the patient populations seen at and referred to the MUST Research Group clinical centers located in the United States, United Kingdom, Australia, Canada, and India.. Typically, patients will be identified in the course of usual clinical practice by the study physicians. When a potentially eligible patient is identified, the study physician and study coordinator will describe the study to and discuss the study with the patient. Patients considering enrollment will be given the consent statement and, if applicable, IRB-approved informational materials and be allowed time to decide about joining the study. After patients have time to review materials and discuss enrollment with family members when appropriate, the clinic coordinator or study physician will obtain written informed consent, using a written, local IRB-approved consent document based on a prototype prepared by the CC and approved by the CC's IRB, the JHSPH IRB Office. The trial will be registered on www.ClinicalTrials.gov. Recruitment efforts and eligibility criteria for MERIT are subject to review and approval by IRBs and the DSMC.

11.2. IRB/Protection of human subjects

Potential risks and procedures to minimize risks to participants

The injection procedures, dosage of medication and treatment algorithm within the study will be consistent with standard clinical treatment, e.g., sterile technique, prophylactic pressure lowering medicine instilled prior to procedure. To minimize risks associated with increased ocular pressure post-injection, patients with uncontrolled ocular hypertension or glaucomatous changes will be excluded from the trial. Patients in the trial will not be exposed to risk beyond what they would be exposed to with standard clinical care for their condition. Adverse events encountered will be managed by the best medical judgment of the treating physician.

Confidentiality

Confidentiality of patient data will be maintained in accordance with legal regulations. Protected health information will be kept in a secure place. Name, social security number, address, and other such personal data will be kept solely at the clinical center where the patient receives her/his clinical care. Such information will not be transmitted to the Coordinating Center or to other study sites. A dataset limited so as to contain a minimal amount of protected health information—that required to make the data useful for accomplishing the purposes of the MUST Trial—may be disclosed, as needed, to collaborating study sites, the NEI, and the FDA, as will be stated on a study privacy acknowledgment form signed by the participant at the time of enrollment. Also included in the privacy acknowledgment is the statement that representatives of NEI, FDA, the Institutional Review Boards, and Coordinating Center may see identifying information while reviewing study records. This privacy acknowledgment will be designed to conform to specifications of HIPAA regulations, and any other relevant regulations, as approved by the local governing authorities invested with oversight of HIPAA regulations at each participating site. Clinically relevant information from the study may be placed in the patient's medical record. Release of protected health information to any other persons or organizations will require additional written consent of the patient affected, except as required by law.

Inclusion of children

Patients under 18 years of age will not be included as neither ranibizumab nor the dexamethasone pellet is approved for pediatric use.

Data and safety monitoring

Trial monitoring will be conducted by a study Data and Safety Monitoring Committee (DSMC). The DSMC consists mostly of members of the standing DSMC which monitored the Multicenter Uveitis Steroid Treatment (MUST) Trial and now is monitoring the MUST Follow-up Study. The Chair of the MUST DSMC, who is a biostatistician, is unable to serve because of potential conflicts of interest. Hence a new member who is an experienced methodologist for ophthalmic studies was appointed and the Chair of the DSMC for this protocol is one of the clinical experts. The committee consists of voting members with expertise in biostatistics, clinical trial design, and ophthalmology who were appointed by NEI and non-voting members (i.e., Study Officers).

For each DSMC meeting, data will be summarized by personnel from the CC and presented to the DSMC. The DSMC will meet at least twice a year (one in-person meeting and one meeting by conference call). Additional meetings/conference calls may be requested by DSMC Chair and/or NEI Project Officer. Meeting reports will include information summaries related to monitoring the safety and effectiveness of the study treatments as well as study performance including data quality and clinic performance. Pertinent information from outside sources such as a reprint of a recent publication reporting on results of other, related studies will also be included as available. All reports will include tables and graphs that summarize and formally compare baseline and adverse event data by treatment assignment, and if indicated, within specific subgroups. A single interim efficacy analysis formally comparing the treatment groups will be performed once 50% of participants have completed the 12-week visit (See Section 10). Graphical and/or numeric summaries (without formal statistical comparisons) will be provided in the meeting books that are not associated with the interim efficacy analysis. Additional efficacy analyses may be performed at the request of the DSMC if necessary.

The DSMC Medical Safety Officer, appointed from among the physician voting members of the DSMC, will review all SAE reports received by the CC as described in section 5.1.

12. References

Bibliography

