5.5.1 Formulation of ranibizumab

Added a note that the volume fill for the ranibizumab vials donated by Genentech for U.S. clinical centers was changed from 0.3 mL to 0.23 mL beginning with the drug distributed in August 2018 but the vial size (0.3 mL) did not change.

10. Efficacy monitoring and stopping guidelines

The time point for the single pre-planned interim efficacy was changed from once 50% to 40% of participants have completed the 12-week visit (the primary outcome time-point). The type I error thresholds were adjusted accordingly to 0.00016 (from 0.00082) at the interim analysis and 0.02484 (from 0.02418) at the final analysis, maintaining a global 0.025 error rate over the course of the trial based upon O’Brien-Fleming boundaries.

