3.1. Type of study

- Randomized, three-arm, parallel design, randomized comparative effectiveness trial
- Randomization stratified by presence or absence of concomitant systemic corticosteroid and/or immunosuppressive therapy for any indication
- Unit of randomization is patient, not eye; if both eyes meet eligibility criteria, both receive same treatment
- Allocation ratio (1:1:1)
- Multicenter
- Fixed sample size, 240 (80 per treatment group)
- Anniversary close-out at the 6-month clinic visit
- Reading center graders and visual acuity examiners will be masked to treatment
- Treating physicians and patients will be unmasked (the intravitreal therapies are different in appearance and have potentially different injection schedules)

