The rates of adverse events will be compared using a Negative Binomial model with a random effect for individual. The overall burden and timing of serious adverse events will be displayed graphically by plotting a single line for each individual highlighting the start and stop dates of SAE sorted by the time of first event¹³³. Robust standard errors will be computed for all analyses using statistical program-based approaches or the bootstrap, where the unit of analysis is the individual. In addition, the models will be adjusted for the stratification variable used during randomization (presence or absence of concomitant systemic corticosteroid and/or immunosuppressive therapy). All primary analyses will be according to treatment assignment (i.e. following the principles of Intention to Treat). A sensitivity analysis of based upon treatment received will be performed for comparison. Additional sensitivity analyses will be performed to assess the impact of missing data. These include 'best' and 'worst' case single imputations as well as multiple imputation and pattern mixture approaches^{134, 135}.

10. Efficacy monitoring and stopping guidelines

The guidelines for the interim efficacy analyses were developed by the Data and Safety Monitoring Committee (DSMC) and MUST Executive Committee. Additional unplanned efficacy analyses will be done if recommended by the DSMC or MUST Executive Committee.

A single pre-planned interim efficacy analysis will be performed once 40% of participants have completed the 12-week visit (the primary outcome time-point). The type I error for each of the co-primary comparisons is 0.025, i.e. half was allocated to each comparison to control the study wide type I error rate. For each comparison, the type I error thresholds would be 0.00016 at the interim analysis and 0.02484 at the final analysis to maintain a global 0.025 error rate over the course of the trial based upon O'Brien-Fleming boundaries.

11. Regulatory and ethical issues

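### The single formal interim efficacy analysis has two triggers in the current text (40% in Section 10, 50% in 11.2), and the stated interim threshold of 0.00016 was set for 40%.

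*Combined protocol and SAP*

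**What the plan says.** **Section 10 (Efficacy monitoring and stopping guidelines).** "A single pre-planned interim efficacy analysis will be performed once 40% of participants have completed the 12-week visit". For each of the two co-primary comparisons, which carry 0.025 each, the thresholds are "0.00016 at the interim analysis and 0.02484 at the final analysis to maintain a global 0.025 error rate over the course of the trial". The boundary family is named only as O'Brien-Fleming; no spending function is written down.

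**Section 11.2 (Data and safety monitoring).** The single interim analysis that formally compares the groups "will be performed once 50% of participants have completed the 12-week visit (See Section 10").

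**Section 3.1.** "Fixed sample size, 240 (80 per treatment group").

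**Revision history, version 1.6, entry for Section 10.** "The time point for the single pre-planned interim efficacy was changed from once 50% to 40% of participants have completed the 12-week visit", with the levels adjusted "to 0.00016 (from 0.00082) at the interim analysis and 0.02484 (from 0.02418) at the final analysis". That version's list has no matching change to 11.2. The log is cited only to show which of the two current passages is out of date.

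**Unplanned analyses.** Section 10: "Additional unplanned efficacy analyses will be done if recommended by the DSMC or MUST Executive Committee". Section 11.2: "Additional efficacy analyses may be performed at the request of the DSMC if necessary". Neither sentence says whether such analyses are descriptive or formal tests.

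**The concern.** The two sections describe the same analysis and cannot both be followed. Section 11.2 is where the protocol sets out what the DSMC will receive, so the DSMC or the Coordinating Center could work from it. The look would then fall at 120 participants, judged against a threshold derived for 96.

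Two things depend on the trigger. One is how early the trial can declare superiority, and with what probability. The other is that the timing of the only planned formal look should be fixed in advance. The DSMC also sees graphical or numeric summaries at its other meetings. With two written triggers, someone could later ask whether the timing was chosen after seeing results, and one trigger removes that question.

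A smaller point sits beside this one. Both sections leave room for further efficacy analyses without saying whether they use up type I error.

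**Working it through.** **Inputs.** Two-sided 0.025 per comparison (9.1, Section 10). Levels 0.00016 and 0.02484 (Section 10). Triggers 40% (Section 10) and 50% (11.2). N = 240 (3.1). Expected reductions of 25% and 38%, and 79 independent eyes per arm (9.1). The SD of 0.33 for change in log thickness is given in 9.1 for the methotrexate-ranibizumab comparison and is assumed here for the primary comparisons. The information fraction t is taken as the fraction of participants with the 12-week visit (assumption).

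**1. Participants at each trigger.** 0.40 × 240 = 96; 0.50 × 240 = 120; difference 24.

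**2. Reproducing the plan's thresholds.** O'Brien-Fleming-type spending, applied as two symmetric one-sided halves:

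α(t) = 4·[1 − Φ(z(1 − 0.025/4)/√t)], with z(0.99375) = 2.498.

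| t | α(t) | 0.025 − α(t) | Where the pair appears |
|---|---|---|---|
| 0.40 | 0.000157 → 0.00016 | 0.02484 | Section 10, current |
| 0.50 | 0.000824 → 0.00082 | 0.02418 | log only, superseded |

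Solved backwards, 0.00016 corresponds to t = 0.401 and 0.00082 to t = 0.4996. No other form tried gives 0.00016 at either trigger. The direct two-sided form, 2·[1 − Φ(z(1 − 0.0125)/√t)], gives 0.00039 at 40% and 0.00153 at 50%. The classical two-look boundary gives 0.00039 and 0.00146.

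**3. Type I error per comparison.** This is the probability that |Z| exceeds its critical value at the interim or the final, with correlation √t between the two statistics. The family-wise column covers both comparisons, correlated 0.5 through the shared control arm, and is simulated.

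| Look | Interim level | Final level | Error per comparison | Family-wise |
|---|---|---|---|---|
| 40% | 0.00016 | 0.02484 | 0.0249 | 4.6% |
| 50% | 0.00016 | 0.02484 | 0.0249 | 4.6% |
| 50% | 0.00082 | 0.02484 | 0.0251 | 4.7% |
| 50% | 0.00082 | 0.02418 | 0.0245 | – |

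The stated pair is slightly conservative because the final level is found by subtraction.

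**4. Chance of crossing at the interim.** The drift is θ = log(0.75/0.62)/(0.33·√(2/79)) = 0.1904/0.0525 = 3.625. This gives 91.7% fixed-sample power at 0.025, against 91% in 9.1. The crossing probability is Φ(θ√t − z), with z = 3.775 for 0.00016 and 3.346 for 0.00082.

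- 40%, 0.00016: Φ(2.293 − 3.775) = 6.9%
- 50%, 0.00016: Φ(2.563 − 3.775) = 11.3%
- 50%, 0.00082: Φ(2.563 − 3.346) = 21.7%

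For at least one of the two comparisons, with both new arms at 38%, the figures are 11.9%, 18.7% and 33.6%. Overall power per comparison is about 91.6% in all three cases.

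**5. Unplanned looks (secondary).** Suppose one further formal look is added at 60%, 70% or 80%, tested at the O'Brien-Fleming-type nominal level (0.00247, 0.00561 or 0.01040), and the final is left at 0.02484. The error per comparison becomes 0.0257, 0.0265 or 0.0276, and the family-wise error 4.8%, 4.9% or 5.1%.

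**The case against.** The strongest reply is that this is a missed update and not a competing plan. Section 11.2 defers to Section 10, only Section 10 carries thresholds, and the version 1.6 log documents a deliberate move to 40%. Section 10 also says the DSMC helped develop the guidelines, so it is unlikely to be misled. The inferential harm is nil, since error and power do not move. The 21.7% figure uses a threshold that survives only in the log, so the contrast available from current text is 6.9% against 11.3%.

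Most of this is fair, and it limits the weight of the point. It does not remove the contradiction. Nothing in the document says which section prevails, and a reader must reconstruct the answer from the change log.

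Two further qualifications stand. First, the match of 0.00016 to 40% depends on one particular spending form, which the plan does not name; the log is independent evidence that the level was set for 40%. Second, the figures for unplanned looks assume formal tests that neither section prescribes. Section 11.2 calls the formal comparison single, which suggests that the others are descriptive. That part is a request for clarity and does not show that error is inflated.

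**Conclusion.** The concern holds. The current text gives two triggers for the same formal analysis, 96 and 120 participants, and the 50% in 11.2 appears to be left over from before version 1.6. As written, 11.2 is wrong against Section 10 and its thresholds.

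The consequence is confined to the timing of the interim and its chance of success: 6.9% against 11.3% per comparison with the stated level, and about three-fold (6.9% against 21.7%) between the two internally consistent designs. With only the planned look, the stated 0.025 per comparison is protected either way.

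The crossing probabilities rest on an SD of 0.33 for the primary comparisons and on information proportional to participants; bilateral eyes could shift the fraction slightly. The contradiction itself rests on neither assumption. The correction should be made, but it does not threaten the trial's primary inference.

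**What to change.** In 11.2, change 50% to 40%, so that it agrees with Section 10 and with 0.00016 / 0.02484.

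If 50% is what the sponsor intends, change Section 10 instead, along with its levels. The choices are 0.00082 at the interim with 0.02418 at the final by the plan's subtraction rule (error 0.0245), or 0.00082 with 0.0247 at the final to reach 0.025.

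In the same edit, add one sentence to Section 10. It should say that any unplanned efficacy analysis is descriptive and cannot support an efficacy claim or stopping for efficacy, unless error is spent by α(t) = 4·[1 − Φ(z(1 − 0.025/4)/√t)] at a time not chosen from observed results and the final level is recomputed. The formula should be written out because the name O'Brien-Fleming alone does not identify it: the direct two-sided form would give 0.00039 at 40%.

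Cost of the preferred option: one number in 11.2 and one sentence in Section 10. Sample size, the Section 10 thresholds and power are unchanged.
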